## 5.0 Potential Risk to Participants

- Confidentiality could be breached, as is a risk in all human subjects research. Sensitive personal health information or other sensitive information could be divulged inappropriately to outside sources.
- Physical functioning testing. Short Physical Performance Battery and hand grip strength testing may involve minimal risk. Risks include muscle soreness, fatigue, and potential muscle strain.
- Injury, pain or fatigue. Participants may experience joint discomfort, muscle soreness, or other minor injuries due to increased physical activity. Cohort 4 the addition of possible skin irritation or other minor injuries due to increased physical activity and the use of therapy.
- Activity monitors such as the Actigraph, Wii Fit meter, and Digit-Walker pedometer, cohort 4 the use of Fitbit or Mi Xiaomi Band 3 are associated with minimal risk. Some participants might feel slight discomfort or skin irritation from the monitors' contact with the skin.
- Embarrassment. Participants may feel embarrassed to share their activity information with other participants.

We believe all identified risks are minimal given the proposed procedures for protecting against risk.

5.1 Protection Against Potential Risks. All study personnel have attended required courses on human subject protection and HIPAA regulations, and certificates of Institutional Review Board training completion are on file at UTMB. Participants that are eligible based on initial screening will be invited to attend an initial session. They will be given a group orientation to the study, including information on all aspects of the study from the principal investigator (PI). They will be able to ask questions at any time. Following this explanation, potential participants will be given informed consent information and forms to sign. After completing this information, they will proceed to the baseline assessment.

- Confidentiality All data collected will remain confidential.
  - Paper copies of screening forms and assessment forms will be kept in a locked file cabinet in the PI's locked office. ID numbers will be used on these forms to match them to individual participants. The database matching ID numbers to identifying information will be individually password-protected and kept separately on the UTMB secured server.
  - As for the web-based questionnaire administered through Assessment

CenterSM, the security statement indicated that the Assessment CenterSM uses role-based permissions that restrict access to participant data and the privacy of data is driven by HIPAA requirements. The Assessment CenterSM is maintained and secured at Northwestern University Research Data Center in Chicago, IL. Detail description of the security measure is described in Appendix H. Briefly, the Northwestern University Research Data Center have secure communication lines in place to prevent the interception of data transmission by utilizing various data encryption technologies (i.e. Secured Socket Layer) and digital certificates; signatures may also be used to encrypt data, validate data integrity, and authenticate the parties in a transaction. The protected health information (PHI) will be stored separately from other survey data. In addition, the PHI will only be collected and transferred only when necessary. Any data that needs to be transferred will be encrypted prior to transfer. All of the participants will be identified by a generic ID generated by the Assessment CenterSM. Furthermore, the Northwestern University Research Data Center has an established infrastructure for confidential data management that includes having secured facilities that are being monitored 24x7, has sophisticated use of firewall technologies, has intrusion detection software, has anti-virus scans, has dedicated database and application servers, has automatic failover design, has real-time monitoring and related technological capabilities. It also is fitted with redundancy for HVAC, power, and fire detection/suppression systems (**Appendix I**).

- The web-based questionnaire will not ask for participant's name. The research staff will provide each participant a unique study identification number. All necessary firewall and password protections will be implemented to store electronic files. The internet will be used to transfer the completed survey from the Assessment CenterSM with study ID to UTMB secured network. The data will also be stored and formatted using SPSS for Windows (version 20) on the secured UTMB network that requires unique username and password.
- Activity monitors will be encrypted to prevent unauthorized viewing of the application data. Participants in the intervention group will be "friends" with one another. Participants will use pseudonyms on the Wii U and Xbox 360 systems, and wearable trackers to provide additional layer of security. All information collected by the Wii Fit meter, wearable trackers, or the Digit-Walker will be generic and related to physical activity—no other health information will be collected on these devices.
- Telemedicine platform and the conference call systems are HIPPA compliant (Appendix J).
- Physical functioning testing. Short Physical Performance Battery (cohorts 1 and 2) and Senior Fitness Test (cohort 3 and 4) and hand grip strength testing will occur at the UTMB sites with trained nursing staff nearby and will be performed by a research coordinator trained in conducting physical assessments. The location of the tests and supervision by medical personnel will ensure that, in the unlikely but possible case of injury, treatment will be immediately available.
- Injury, pain or fatigue. Walking and low impact activity that will be performed via Wii U and Xbox 360 system, and performing grip strengthening using theraputty and home-based exercise may produce minor injuries. We will reduce the risks for such events by providing detailed protocols and instructions that increase in difficulty slowly over time and that include adequate warm-up and cool-down. The home-

based grip strengthening is not contraindicated for use with breast cancer survivors. An Occupational Therapist will oversee and provide instructions to participants. During the weekly session, study staff will inquire about the participants' walking plans and how participants feel during exercise. Immediate steps will be taken if there is any indication of potential adverse events. (see data safety and monitoring plan).

- Activity monitors. We will warn participants of the risk of potential skin irritation due to wearing the measurement equipment and using theraputty. We will also provide participants with several alternative procedures that could be used to minimize discomfort, such as inserting a soft cloth between the monitor and the skin and alternative exercises for gripping.
- Embarrassment. We will provide training and discussion during the orientation on the importance of confidentiality and privacy. All participants will use pseudonyms when logged into the Wii U system to ensure that their activity information cannot be connected to their true identity.

5.2 Potential Benefits of the Proposed Research. Physical activity interventions may improve mood, fatigue, and overall health.

5.3 Importance of Knowledge to be Gained. There is a need for better understanding of strategies for increasing physical activity among breast cancer survivors. Successful intervention on these behaviors could have a large positive public health impact. If effective, implementing the physical activity intervention using commercially available active games are scalable for wide dissemination to other breast cancer support groups.

## **6.0 Study Withdrawal/Discontinuation**

A study participant will be discontinued from participation in the study if any of the following occur:

- Serious adverse event (SAE)
- Medical condition or situation occurs that prohibits the participant to participate in intervention activities and would not be in the best interest of the subject in the opinion of the PI/treating medical staff
- Participant withdraws consent to continue in the research for any reason

6.1 Handling of Withdrawals. If participants withdraw from the study because of an SAE they will receive a follow up phone call by study personnel to collect safety data. If voluntary withdrawal occurs, study personnel will attempt to contact the participant for return of study equipment.

6.2 Termination of Study. This is a low risk study. We cannot foresee any reason to terminate the research. Individual participants will be discontinued from the protocol if they develop serious medical or psychiatric symptoms that necessitate their removal from the study. In such cases participants will be referred to appropriate care in their community.

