that can be used by BC support groups to encourage physical activity among women BC survivors. Evidence-based strategies such as setting goals, self-monitoring, giving feedback on progress, and using group-based video game play to increase motivation to be active will be included.

The UTMB Breast Cancer Support Group is an excellent intervention partner for three main reasons. **First**, the UTMB Breast Cancer Support Group is facilitated by the experienced clinical staff of the UTMB Breast Health and Imaging Center at Victory Lakes. Currently the group provides informational and peer support for BC survivors and is respected by the community. **Second**, the UTMB Breast Health and Imaging Center that has become a premier BC care center for residents in Galveston County area and its affiliated support group is well known in the community. By building a partnership between researchers and stakeholders—clinicians, staff, and survivors—we will be able to disseminate effective physical activity interventions or programs that will serve the BC survivor community and increase the center’s community outreach capacity. **Third**, clinic staff report a need for a structured curriculum that uses physical activity to help BC survivors cope with their treatment. Thus, the *Pink Warrior* intervention will address this existing need in the community. By using support group facilitators to promote physical activity, we will be able to reach more BC survivors during and after active cancer treatment to prevent significant physical function declines and positively impact BC survivors’ quality of life.

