**Aim 2: Compare the support group using the active video game-based physical activity intervention (intervention group) to the existing UTMB breast cancer support group with pedometer (control group for cohorts 1-3) or the telephone-based support group with the UTMB support group (control group for cohort 4).** We will use analysis of covariance (ANCOVA) to test the post-intervention differences at 12-weeks (physical activity) between the two groups, controlling for baseline and other covariates that are significantly different at baseline. Intent to treat analysis will be used to handle missing data. ANCOVA will also be used to evaluate the secondary outcomes (physical function and quality of life). We will explore the changes in psychosocial variables using linear mixed models to investigate differences between groups and over here time points. Since this is a pilot study and it is not powered to detect significant differences of small to moderate effects, we hypothesized that the intervention group will show an improvement in physical activity, physical function, and quality of life compared to the control group. We also hypothesize that the intervention group will show an improvement in self-reported scores on self-efficacy, self-regulation, intrinsic motivation

**Aim 3: Develop tools for implementation of the Pink Warrior intervention within the clinic and community settings.** Development of a trainer's manual for the intervention will mainly be based on descriptive analyses using the facilitator's weekly group log. The facilitators will indicate whether or not they were able to cover the entire session as planned and facilitator will also be asked to provide feedback regarding the facilitator's guide and their feedback regarding the group activities.

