**9.1 Plan for data management.** For self-report and feasibility data, the PI is responsible for collection and storage of data initially on electronic questionnaires and saved assessment information from the paper format, then transferred to a computer database located on a secure UTMB server. Questionnaire data will not be personally identifiable. All questionnaires will use ID numbers for identification purposes, and the correspondence of ID numbers to names will be kept in a password-protected file on a password-protected, secure server. Databases will use ID numbers for identification of data and will also be stored on the secure, password-protected server. The data collected by the game consoles will not be directly linked to the participants because pseudonyms were provided for each participant. Data saved by the game consoles will be moved and erased from the console prior to further use of the console or provision to another participant.

**9.2 Plan for adverse event reporting.** The PI will also hold responsibility for monitoring and reporting adverse events of any kind. We do not anticipate severe adverse events, though mild and moderate events are possible. The scale to be used is the UTMB Clinical Research Center Adverse Event Grading Scale (Table 5). Examples of each level of adverse event on the scale are provided below.

- **Mild** events include discomfort without disruption of daily activities. No therapy or only symptomatic therapy is required. This level is equivalent to NCI Common Terminology Criteria for Adverse Events version 4.03 Grade 1 adverse events (mild; asymptomatic or mild symptoms; intervention not indicated).
- **Moderate** events include discomfort sufficient to modify daily normal activity. Specific therapy is required. Laboratory test alterations indicate injury without long-term risk. This level is equivalent to NCI Grade 2 (moderate; minimal, local or noninvasive intervention indicated; limiting age-appropriate activities of daily living).
- **Severe** events include incapacity, inability to work, inability to perform normal daily activity, hospitalization required, prolonged emergency treatment required, life-threatening events, laboratory tests indicating a serious health threat or permanent injury, and death. This level is equivalent to NCI Grades 3 (severe/medically significant but not immediately life-threatening), 4 (life-threatening, urgent intervention indicated), and 5 (death).

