**Table 5. Reporting of adverse events to IRB**

NCI Adverse Event Grade	Expected	Unexpected
Grade 1	Reporting not required	Report within 10 days
Grade 2	Reporting not required	Report within 10 days
Grade 3 (UTMB level 3)	Report by phone within 24 hours	Report by phone within 24 hours
Grade 4 (UTMB level 3)	Report by phone within 24 hours	Report by phone within 24 hours
Grade 5 (UTMB level 3)	Report by phone within 24 hours	Report by phone within 24 hours

The PI will follow the reporting requirements for serious and unexpected adverse events outlined in the UTMB IRB Adverse Event Policy. All unanticipated, serious, fatal, and/or life-threatening adverse events will be reported to the UTMB IRB within 24 hours of occurrence or recognition. Aggregate reports of adverse events will be prepared on an annual basis and forwarded to the IRB at annual review.

Attribution will be assessed by the PI on a scale used by CRC investigators: 1) not related, 2) possibly related, 3) probably related, 4) definitely related to the study interventions.

9.3 Protection of human research participants – computer-based training. All research personnel have completed the UTMB required training course in protection of human research participants.

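### Section 6.0 takes a woman out of the study, not only the intervention, after an SAE or a prohibiting medical condition, and nothing provides for her week 14 outcome

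*Combined protocol and SAP*

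**What the plan says.** Section 6.0 opens with "A study participant will be discontinued from participation in the study if any of the following occur". Three triggers follow. The first is an SAE, with no condition on relatedness. The second is a medical condition or situation that "prohibits the participant to participate in intervention activities and would not be in the best interest of the subject", in the opinion of the PI or treating staff. The third is withdrawn consent.

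Section 6.1 covers what happens next. After an SAE, "they will receive a follow up phone call by study personnel to collect safety data". After voluntary withdrawal, staff try to recover the equipment. Nothing is written for a woman discontinued under the medical trigger.

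Section 6.2 adds: "Individual participants will be discontinued from the protocol if they develop serious medical or psychiatric symptoms that necessitate their removal from the study". She is then referred for care.

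In Section 7.0 (Aim 2), post-intervention physical activity is compared by ANCOVA adjusted for baseline, and "Intent to treat analysis will be used to handle missing data". Section 4.6 takes the activity comparison from baseline to week 14, with a further monitor week at week 7. Section 7.1 uses the results to set effect sizes for larger trials and wants a Cohen's d from cohort 4 by itself.

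**The concern.** Stopping the exercise programme for safety is right. Stopping measurement as well is a separate decision, and Section 6.0 takes both at once. The SAE and medical triggers do not depend on withdrawn consent, so the outcomes lost through them are partly avoidable.

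The SAE trigger is broad as written. Section 9.2 has relatedness graded ("Attribution will be assessed by the PI on a scale used by CRC investigators"), but Section 6.0 does not use that grade. Section 2 says of the programme that "we will be able to reach more BC survivors during and after active cancer treatment", so admissions unconnected with the intervention are conceivable in either arm.

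The medical trigger is tied to intervention activities, and only the intervention arm has group exercise sessions, so losses could differ by arm. Women who leave for health reasons are also unlikely to be typical in their step counts. What is at stake is the randomised comparison at week 14, and the effect sizes carried forward from it. In cohort 4 one woman is 10% of an arm.

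**Working it through.** **Step 1: is there any route to her week 14 value?**

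- Sections 6.0 and 6.2 end participation in the study or protocol.
- Section 6.1 provides a safety call or equipment recovery, and no outcome assessment.
- Section 4.6 and Tables 3a and 3b give the assessment schedule, with no rule for discontinued women.
- Section 4.7 allows contact to arrange monitor drop-off before week 14, again without mentioning them.
- The Data and Safety Monitoring Plan says that all planned variables must go on being measured at each time point. There it explains why the periodic safety reviews omit a full analysis. It does not mention discontinued women or override Section 6.0.

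Loss of the week 14 value is therefore a strong inference, not a stated rule.

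**Step 2: what happens to her in the analysis?** Section 7.0 names intention to treat as the way to handle missing data, but gives no imputation or model. Omission is one possible result. A woman removed after week 7 may have a post-baseline monitor value, which some methods could use.

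**Step 3: how large could the bias be if she were dropped?** The plan's N of 60 cannot be reproduced, because no SD, alpha or power is given, and this point does not depend on it.

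*From the documents:* arms of 10 (cohort 4), 5 + 5 + 20 = 30 (cohorts 1-3), and 30 + 10 = 40 if all are pooled. No pooled model is stated.

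*Assumed, without a source in the documents:* baseline SD 2,000 steps/day, slope 0.6, residual SD 1,600, hence outcome SD = √(0.36 × 2,000² + 1,600²) = 2,000; a gap between women who stay and women removed of 1,000, 2,000 or 3,000 steps/day; and the numbers removed.

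If k1 and k0 women are removed from the intervention and control arms, each of size n:

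bias = (k1 − k0)/n × gap; SE of the difference = 1,600 × √(2/n)

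| Case | SE | Bias at gap 1,000 / 2,000 / 3,000 | Bias ÷ SE |
|---|---|---|---|
| Cohort 4, n = 10, 1 vs 0 | 716 | 100 / 200 / 300 | 0.14 / 0.28 / 0.42 |
| Cohorts 1-3, n = 30, 1 vs 0 | 413 | 33 / 67 / 100 | 0.08 / 0.16 / 0.24 |
| Pooled, n = 40, 1 vs 0 | 358 | 25 / 50 / 75 | 0.07 / 0.14 / 0.21 |
| Pooled, n = 40, 4 vs 2 | 358 | 50 / 100 / 150 | 0.14 / 0.28 / 0.42 |

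On the d scale (divide by 2,000), the cohort 4 bias is 0.05 / 0.10 / 0.15, against an SE of 716/2,000 = 0.36. The bias is zero if removals and gaps match across arms, and changes sign if the control arm loses more. Simulation of complete-case minus full-data ANCOVA (4,000 runs per case) agreed to within about 3 steps. That confirms the formula; it is not evidence that removals occur.

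**Step 4: carry-forward, both signs.** Take a true difference of 1,000 steps (d = 0.50), which needs 64 per arm for 80% power (t-test, two-sided 5%). The pooled one-removal bias in d is 25/2,000 to 75/2,000 = 0.0125 to 0.0375.

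- Intervention arm loses one more: d reads 0.5125 to 0.5375, so 61 to 56 per arm and true power 78% to 75%.
- Control arm loses one more: d reads 0.4875 to 0.4625, so 68 to 75 per arm and true power about 82% to 86%.

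**The case against.** The strongest reply is that the harm needs two inferences: that no outcome is collected, and that the woman is then omitted. The second is not in the plan. An intention-to-treat label, however vague about method, points towards keeping randomised women in. This stands: a reader might infer that the plan runs a completers' analysis under an intention-to-treat name, and the documents do not support that. The unnamed missing-data method is a separate gap.

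Next, the rule may seldom operate. The monitoring plan expects no SAEs, the study is called low risk, the medical trigger needs a judgement as well as a condition, and Section 6.2 speaks of symptoms that make removal necessary. A reader might infer that any hospital admission removes a woman. Section 9.2 does put "inability to perform normal daily activity, hospitalization required, prolonged emergency treatment required" in its severe grade, but the documents never define an SAE for Section 6.0, and a severity grade is not that definition. What remains is that the SAE trigger itself contains no judgement, so Sections 6.0 and 6.2 do not give staff one rule.

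Third, a reader might infer that the effect would be inflated. Nothing fixes the direction: Step 4 gives errors either way. Sampling error exceeds the bias in every case tabulated, and the 3,000-step gap is 1.5 assumed outcome SDs.

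Last, women too ill to continue may not reach 10 hours of wear on at least 4 days. That limits what the fix recovers, but does not remove the reason for asking.

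**Conclusion.** The point holds as a gap in follow-up. Section 6.0 ends study participation for two health-related reasons that do not require withdrawn consent, and no section provides for the week 14 outcome afterwards. The value would probably be missing from the ANCOVA; whether the woman is then omitted is not settled by the plan.

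The resulting bias has unknown size and sign and is probably small. The documents give no removal rate, SD or step gap, so every figure above is hypothetical and assumes a complete-case analysis that the plan does not state. On those inputs the bias is at most 0.42 of a standard error. The case for acting rests on a clear gap and a low price, not on a large effect. Low severity: a cheap improvement.

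**What to change.** In Sections 6.0 to 6.2, for the SAE and medical triggers, replace discontinuation from the study with discontinuation of intervention activities, as judged by the PI or treating staff. Then state:

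- Unless she withdraws consent for data collection or treating staff object, she is invited to the scheduled week 14 activity monitor and questionnaires, and to week 7 where feasible.
- Mail, drop-off or telephone may be used. Section 4.6 now links telephone interviews to pandemic restrictions, and Section 4.7 links monitor drop-off to week 14, so both need extending to these women.
- No physical function tests are required of her.
- She is analysed in the arm to which she was randomised. If the wear rule is not met, her monitor steps stay missing; in cohort 4 the week 14 CHAMPS questionnaire still gives self-reported activity.

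For cohorts already completed, report health-related discontinuations by arm and reason. A sensitivity analysis that shifts missing week 14 steps is optional. Its offsets should be labelled as assumptions and applied in both directions.

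The cost is protocol wording, possibly matching consent wording (the consent form is not among the documents reviewed), and a few extra assessments. There is some burden on women who are unwell, and some monitor weeks will be invalid. Follow-up changes mainly for cohort 4 (N = 20).

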## 1. Specific Aims

Increasing and maintaining physical activity among female breast cancer (BC) survivors remains an unresolved problem in BC survivorship care. BC survivors, from diagnosis until the end of life, go through many transitions. One major transition is the significant decline of physical activity immediately after diagnosis. Despite the known benefits of PA—speeding recovery time and reduced cancer recurrence risk—less than 30% of survivors met PA recommendations. PA interventions have shown effectiveness in helping BC survivors increase PA, but limited evidence-based PA interventions have been disseminated into the clinic and community. To address this limitation, we are partnering with the UTMB breast cancer support group to conduct a 12-week physical activity intervention, *Pink Warrior*, which will investigate the feasibility of implementing active video game-based physical activity intervention among BC survivors within the support group setting. In cohort 1-3 participants (N = 60) will be randomized to participate in the support group using the active video game-based physical activity intervention or to participate in the existing UTMB breast cancer support group with pedometers. In the fourth cohort, participants (N=20) will be recruited and randomly assigned to intervention or control condition.

Our specific aims are:

**Aim 1: Evaluate the feasibility and acceptability of active video game-based physical activity intervention among BC survivors within the support group setting.** Measures of feasibility will include weekly attendance records, number of completed home-based worksheets, and number of participants completing the program activities, technological issues, and adverse events.

**Aim 2: Compare the support group using the active video game-based physical activity intervention to a control condition (cohort 1-3: existing UTMB breast cancer support group with pedometer; cohort 4: Telephone-based weekly support group with UTMB support group).** Primary outcomes will be changes in physical activity. Secondary outcomes will be changes in physical function, dietary pattern, and quality of life.

**Aim 3: Develop tools for implementation of the Pink Warrior intervention within the clinic and community settings.** A trainer's manual for the Pink Warrior intervention will be developed and UTMB Breast Cancer Support Group facilitators will be trained by research staff to implement the program.

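### Section 6.1 plans no safety enquiry and no record of the reason at voluntary withdrawal, so the Aim 1 adverse event count may be too low

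*Combined protocol and SAP*

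**What the plan says.** Section 6.1 (Handling of Withdrawals) has two rules. For withdrawal because of an SAE: "If participants withdraw from the study because of an SAE they will receive a follow up phone call by study personnel to collect safety data". For voluntary withdrawal: "If voluntary withdrawal occurs, study personnel will attempt to contact the participant for return of study equipment". The list of discontinuation grounds in section 6.0 makes the second group broad: "Participant withdraws consent to continue in the research for any reason".

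Section 5.0 describes the harms that the plan has in mind: "Participants may experience joint discomfort, muscle soreness, or other minor injuries due to increased physical activity". The Data and Safety Monitoring Plan (numbered 9.0 in the text) likewise lists mainly minor anticipated events and does not expect serious ones.

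Section 1, Aim 1, counts among the feasibility measures the "number of participants completing the program activities, technological issues, and adverse events". Section 4.6 repeats adverse events as a feasibility measure, including for cohort 4.

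On asking about symptoms while a woman is attending, section 5.1 says: "During the weekly session, study staff will inquire about the participants' walking plans and how participants feel during exercise".

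**The concern.** The planned safety call covers the type of exit at which the event is already known. It does not cover the type at which an expected, minor event might still be unknown. A woman who strains a joint during home-based activity and then withdraws consent is a voluntary withdrawal under section 6.0, and the only contact stated for her is about equipment.

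Three uses of the data are affected.

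- **The Aim 1 count.** An event that nobody records cannot enter it.
- **Reading of non-completion.** Programme completion is also an Aim 1 measure. Without a recorded reason, drop-out linked to harm cannot be separated from drop-out for other causes.
- **Event handling.** The monitoring plan requires attribution and risk/benefit impact to be judged for each event, and Table 5 requires unexpected Grade 1 and 2 events to be reported within 10 days. Neither can happen for an unrecorded event.

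The feasibility findings are meant to guide refinement of the programme for larger efficacy trials, so a tolerability summary with an unknown gap would be carried forward.

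**Working it through.** **1. Is there a figure to reproduce?** No. The documents give no adverse event rate, no target count and no withdrawal rate after randomization. The drop-out allowance in section 4.2 (160 recruited to randomize 80) concerns losses between screening and randomization. The check therefore rests on the text.

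**2. Each route by which a minor event could be recorded, tested on a woman whose event follows her last attended session and who then withdraws.**

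- *Section 6.1, SAE call.* Does not apply; her event is not serious.
- *Section 6.1, voluntary withdrawal.* Contact is attempted, but the stated purpose is equipment.
- *Section 5.1, enquiry at the weekly session.* Reaches her only at sessions she attends. Section 4.4 places part of the programme at home, so events can arise between sessions.
- *Tables 3a and 3b, week 7 and week 14.* She has been discontinued from participation, and no later assessment is planned for her. Neither table lists an adverse event item.
- *Data and Safety Monitoring Plan, coordinator's duty to enquire and document.* General and not limited to women still attending, but with no timing and no link to withdrawal.
- *Data and Safety Monitoring Plan, review of logs and data by the principal investigator.* Covers what has already been collected.
- *Section 4.7, unscheduled contact.* Optional, and prompted by an existing question or concern.

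Some of these routes could capture the event, but none is scheduled to do so.

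**3. Direction.** Missing events can only lower the count.

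**4. Size: illustration only, on assumed inputs.** Let N be the number randomized, w the share who withdraw voluntarily, p the event risk in completers, RR the relative event risk in withdrawers, and m the share of withdrawers' events that is not captured.

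- True number with an event = N[(1 − w)p + w·p·RR]
- Recorded number = N[(1 − w)p + w·p·RR(1 − m)]
- Shortfall as a share of the true number = w·RR·m / [(1 − w) + w·RR]

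Only N = 80 comes from the documents (section 4.2). Assume w = 20%, p = 10% and RR = 2:

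- Completers: 80 × 0.80 × 0.10 = 6.4
- Withdrawers: 80 × 0.20 × 0.10 × 2 = 3.2
- True number: 6.4 + 3.2 = 9.6
- Recorded: 9.6 − 0.25 × 3.2 = 8.8 (m = 25%); 9.6 − 0.50 × 3.2 = 8.0 (m = 50%); 9.6 − 3.2 = 6.4 (m = 100%)
- Shortfall: 0.8/9.6 = 8%; 1.6/9.6 = 17%; 3.2/9.6 = 33%

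Over w = 10–30%, RR = 1–3 and m = 25–100%:

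- Lowest: 0.10 × 1 × 0.25 / (0.90 + 0.10) = 2.5%
- Highest: 0.30 × 3 × 1 / (0.70 + 0.90) = 0.90/1.60 = 56%
- With no excess risk in withdrawers (RR = 1) the shortfall is w × m, from 2.5% to 30%
- With full capture by the other routes (m = 0) it is zero

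The range reflects the assumptions and does not estimate what this trial will lose.

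**The case against.** The strongest reply is that section 6.1 deals with withdrawal logistics, and that adverse event capture belongs to the monitoring plan. There the coordinator must enquire and document, all personnel watch for events, and the principal investigator is responsible for adverse events of any kind. Section 4.7 lets staff contact participants about adverse events, and nothing forbids a question about harm during the equipment call. This stands to the extent that capture may be better in practice than section 6.1 suggests. It does not supply a scheduled enquiry at withdrawal, and section 6.1 is the specific instruction that staff will follow when someone leaves.

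Second, missing sessions is not withdrawing consent. A woman who stays away because she is sore keeps her week 7 and week 14 assessments. An injury that prevents participation may also fall under the separate medical-condition ground in section 6.0, where staff would know of it (although section 6.1 states no safety call for that ground either). Both points stand, and they narrow the gap to women who actually withdraw with an event not already raised.

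Third, Aim 1 is descriptive and has no adverse event threshold, so a few more mild events would trip no stated rule. That is correct and limits the consequence. The count is still a stated outcome and should be complete or qualified.

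Fourth, limiting contact after consent is withdrawn is defensible in a low-risk study. But the plan already intends to make contact, and optional questions respect the participant's choice.

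**Conclusion.** The gap is real but limited. Section 6.1 treats SAE and voluntary withdrawals differently, and no section schedules a safety enquiry or a record of the reason at or after voluntary withdrawal. A non-serious event after the last attended session may therefore go unrecorded, and the Aim 1 count may be too low. Any resulting error in the count is downward; its size cannot be determined from the documents.

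A reader might infer more, in three ways that the documents do not support.

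- *That women who leave are never asked about harm.* They are asked at the weekly sessions they attend, and other contact is possible.
- *That withdrawers are the women most likely to have been hurt.* This is plausible, but the documents hold no data on it.
- *That the count is definitely too low, by some stated percentage.* Withdrawal rate, event risk and capture rate are all unknown, and the shortfall is zero if the other routes work fully.

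The point merits a change because adverse events are a stated outcome and the remedy is small.

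**What to change.** In section 6.1, state that the contact already planned for equipment return will be used in every voluntary withdrawal, in both arms, to ask two questions that the participant may decline:

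1. the reason for stopping;
2. any injury, pain, skin problem or other health event since the last contact.

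Grade any event on the section 9.2 scale and include it in the Aim 1 adverse event total. Report, by arm, the number of withdrawals with an event, without an event, and not reached or declined. Reporting by arm matters because section 4.5 plans monthly group contact for controls in cohorts 1–3, while the intervention arm meets weekly, so capture before withdrawal may differ.

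The cost is two questions on an existing contact and a few lines in the Aim 1 summary. The downsides are a slightly higher reported event count and incomplete reach, since some women will not be reached or will not answer. The change affects data collection only.
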